9. STUDY DRUG MATERIALS AND MANAGEMENT

9.1. Description of Study Drug

The study medication is described in Table 6.

Table 6: Investigational Product

Attribute	Investigational Product	
Product name	Dasotraline 2 mg	Matching Placebo
Dosage form	Capsules	Capsules
Unit dose	One capsule	One capsule
Route of administration	Oral	Oral
Physical description	Swedish orange, size #4	Swedish orange, size #4

In addition to dasotraline, the active ingredient, each capsule contains: Mannitol United States Pharmacopeia (USP), Sodium Starch Glycolate NF, Talc USP, and Magnesium Stearate NF.

The matching placebo capsule is identical to dasotraline in color, shape, size, and packaging and contains all ingredients, except the active dasotraline.

9.2. Study Drug Packaging and Labeling

9.2.1. Package Description

Study drug will be provided in 1 week blister cards containing 10 capsules of dasotraline 2 mg or placebo capsules (7 days + 3 extra days).

9.2.2. Labeling Description

All packaging for the study drug will be labeled with:

- Protocol number
- Sponsor's name and address
- Content (eg number of capsules)
- Investigational New Drug statement
- Instructions for use and storage
- Blank space for subject identifiers
- Batch number
- Unique medication number

9.3. Study Drug Storage

All study medication should be stored at USP Controlled Room Temperature: 20°C - 25°C (68°F - 77°F); excursions permitted to 15°C - 30°C (59°F - 86°F). The subject's parent(s)/legal guardian(s) will be instructed to store the study medication at room temperature.

In addition, the subject's parent(s)/legal guardian(s) will be instructed to store the study medication in a location where it cannot be inadvertently accessed and consumed by the subject and to remove all other ADHD treatments from the subject's access.

9.4. Dispensing of Study Drug

An Interactive Response System (IXRS) will be used to manage subject screening and enrollment. The IXRS is an integrated web-based subject and drug management system. Specific User Manuals will be supplied.

Study medication blister cards will be assigned by the IXRS based on the treatment schedule. The IXRS will generate instructions on which medication number to assign to a subject. Appropriate guidelines should be followed in proper dispensation to the study participant. Each subject will be dispensed two 1-week blister cards on Day 1. Proper accountability records must be maintained and accurately document all drug dispensing activities.

Under supervision from the subject's parent/legal guardian, subjects will self-administer the study drug on an outpatient basis (see [Section 10.1](#)). The daily dosage (one capsule) will be clearly labeled on the study drug blister card.

9.5. Study Drug Accountability

The Investigator or designee is responsible for storing the drug in a secure location and for maintaining adequate records of drug disposition that includes the dates, quantity, and use by subjects. If the study is stopped for any reason or completed, all unused supplies of drug will be returned to the Sponsor, unless other instructions are provided in writing by Sponsor/ clinical research organization (CRO).

Upon receipt of clinical trial material (CTM) the Principal Investigator, or designee, will inventory the supplies and verify receipt of supplies. The site will send an Acknowledgement of Receipt to Sunovion Pharmaceuticals, or designee, confirming date of receipt, inventory, and condition of CTM received.

The Investigator, or designee, agrees to collect and document all used and unused study medication from study subjects/parents/legal guardians at appropriate study visits.

Study drug will not be dispensed to any person who is not a study subject under this protocol.

On Day 1 a dosing diary will be provided to the parent/legal guardian to record the date and time of each administration of study drug. On Day 15 the parent/legal guardian will bring the dosing diary to the visit. Only the date and time of the Day 14 dose will be entered into the database.

9.6. Study Drug Handling and Disposal

A drug inventory record will be supplied by the Sponsor/CRO. The Investigator or designee on an ongoing basis must maintain a drug inventory record of supplied, received, dispensed, and returned study drug. The Investigator or designee is required to return all unused supplies of study drug as well as empty packaging from used study drug to the Sponsor or designee as instructed. The Investigator or designee is required to maintain copies of medication shipping receipts, drug accountability records, and records of return or final disposal of the study drug in accordance with local regulatory requirements.

10. TREATMENT OF SUBJECTS

10.1. Study Medication

As described in [Section 7.2.1](#), subjects will be randomized to 1 of 2 treatments (2 mg/day dasotraline or placebo).

Under supervision from the subject's parent/legal guardian, subjects will self-administer the study drug on an outpatient basis for 14 days beginning the evening of Day 1. Study drug should be taken at approximately the same time each evening. The first dose of study drug may be administered in the clinic, at approximately 8 PM plus or minus 30 minutes, after all assessments are completed, before the subject leaves, or at home. On Day 14, the night before the second classroom day, study drug must be taken at approximately 8 PM plus or minus 30 minutes. All study medication doses will consist of 1 capsule per day taken by mouth.

Subjects may take study drug with or without food.

Study drug capsules should not be opened or tampered with in any way; the active ingredient is an ocular irritant.

10.2. Treatment Compliance

During the double-blind period, the clinical site will attempt to contact the subject's parent/legal guardian daily with a reminder to administer study drug.

The Investigator will record the dose of the study drug and the dates of the initial and final administration for each dose.

Compliance with study drug will be monitored closely and determined at each visit. Subjects and their parent(s)/legal guardian(s) will be instructed to bring all unused study drug with them to the Day 15 visit. Compliance will be assessed by counting capsules and dividing the actual number of doses taken (per capsule count) by the number of doses the subject should have taken within a visit period and multiplying by 100. Subjects who miss more than 25% of scheduled doses or take more than 125% of the scheduled doses will be considered noncompliant. Evidence of noncompliance must be immediately reported to the Medical Monitor. Potential noncompliance will be discussed with subjects and their parent(s)/legal guardian(s), and at the investigator's discretion may result in termination of the subject from the study. All subjects and their parent(s)/legal guardian(s) will be reminded of the importance of strict compliance with taking study drug for the effectiveness of treatment and for the successful outcome of the study.

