4.3. Risk-Benefit Assessment

There are two recently completed studies in children with ADHD that report on the efficacy and tolerability of dasotraline (SEP360-202 and SEP360-305), both of which demonstrated statistically significant improvement compared to placebo at the 4 mg/day dose. A third study, SEP360-310, has been completed but the analyses are not yet finalized.

SEP360-202

SEP360-202 evaluated the efficacy and safety of 2 doses of dasotraline (2 mg/day and 4 mg/day) in pediatric subjects with ADHD. In this 6-week double-blind, placebo controlled trial, dasotraline (4 mg/day) was superior to placebo, and well tolerated.

In SEP360-202, overall, 54.1% of subjects experienced at least 1 Treatment Emergent Adverse Event (TEAE) during the study, 38.6% experienced a TEAE that was considered by the Investigator to be related to study drug, and 6.7% experienced a TEAE that led to discontinuation of study drug. Subjects in the dasotraline 4 mg/day group experienced more

TEAEs, more related TEAEs, and more TEAEs that led to a discontinuation than the dasotraline 2 mg/day group and the placebo group, and the placebo group experienced the least in each of these categories. No subjects experienced an SAE and there were no deaths during the study.

SEP360-305

SEP360-305 evaluated the efficacy and safety of dasotraline (4 mg/day) to placebo, in pediatrics with ADHD in a classroom laboratory setting over 2 weeks. The dasotraline (4 mg/day) dose demonstrated statistically superior efficacy when compared to placebo, and was well tolerated.

In SEP360-305, TEAEs were more common in patients taking dasotraline compared with those taking placebo (data from the discontinued 6 mg arm of this trial are included here for safety consideration). TEAEs were generally mild or moderate in severity. Four patients receiving dasotraline experienced severe TEAEs: 4 mg/day: 1 case of insomnia and 1 case of decreased appetite; 6 mg/day: 2 cases of insomnia. No serious AEs occurred in patients treated with dasotraline. TEAEs associated with discontinuation were hallucinations (2 cases in the 6 mg/day group, 1 case in the 4 mg/day group), insomnia (1 case in the 4 mg/day group), decreased appetite (1 case in the 6 mg/day group), and rash (1 case in the 4 mg/day group).

Moreover, there have been three studies of dasotraline efficacy and tolerability in adults with ADHD including one long term de novo trial for safety; SEP360-201, SEP360-301, and SEP360-304 respectively.

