One study was completed that evaluated the safety, tolerability, pharmacokinetic, and pharmacodynamic properties of dasotraline in pediatric (6 – 12 years) and adolescent (13 - 17 years) subjects with ADHD. In this multicenter, open-label study 105 subjects were assigned to single oral doses of dasotraline 1 - 16 mg in a dose-escalating manner. Dasotraline was characterized by slow absorption (median t_{max} was 9.6 to 12 hours) and elimination (median $t_{1/2}$ was 56 to 84 hours) in both pediatric and adolescent subjects. The change in C_{max} with dose was slightly greater than dose proportional. Increase in overall exposure (AUC) with dose was greater than dose proportional. Apparent oral clearance was highest in the lowest dose group relative to the higher dose groups. No deaths, serious adverse events (SAE), or discontinuations because of an adverse event (AE) were reported in this study. The most frequently reported AE by investigators were tachycardia (25 subjects; 23.8%) and electrocardiogram QT prolonged (5 subjects; 4.8%), nearly all of which were considered related to study drug and mild in severity. Tachycardia AEs were reported in both age groups and in every dose cohort. Most events of tachycardia were reported on the day of study drug administration. No subjects experienced QT prolongations > 500 msec. Based on the centrally read electrocardiogram (ECGs) in the study, no clinically significant trends were identified within the ECG results. Blood pressure increased, blood pressure systolic increased, blood pressure orthostatic abnormal, and orthostatic hypotension AEs were reported in 1 subject each. Overall, after dosing, 90 subjects (85.7%) met predefined criteria for orthostatic tachycardia and 40 (38.1%) met predefined criteria for orthostatic hypotension.

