Double-blind Period: On Day 1 subjects will return to the clinic in the morning, and those meeting all inclusion and no exclusion criteria will be randomized (1:1) to receive 2 mg/day dasotraline, or placebo, and will attend classroom sessions in which they will be evaluated for ADHD symptoms using the SKAMP assessment. During this baseline classroom assessment (Day 1), subjects will be evaluated at regular intervals: approximately 8 AM, 10 AM, 12 PM, 2 PM, 4 PM, 6 PM, and 8 PM. Subjects will begin taking study drug on the evening of Day 1 (with or without food) after the final, 8:00 PM baseline classroom assessment. Subjects will take one dose each evening before bedtime for a total of 14 days. Study drug should be taken at approximately the same time each evening. The first dose of study drug may be administered in the clinic after all assessments are completed and before the subject leaves, or at home. On the night (Day 14) before the second classroom day, study drug must be taken at approximately 8 PM plus or minus 30 minutes. During the double-blind period, the clinical site will attempt to contact the subject's parent/legal guardian daily with a reminder to administer study drug. A dosing diary will be provided to the parent/legal guardian to record the date and time of each administration of study drug. On Day 15 subjects will return to the clinic in the morning at 6:30 AM and classroom sessions will be started at approximately 8 AM, 10 AM, 12 PM, 2 PM, 4 PM, 6 PM, and 8 PM to coincide with 12, 14, 16, 18, 20, 22, and 24 hours following the Day 14 dose.

End of Study: Seven (± 2) days after the last dose of study drug, all subjects will return to the clinic and complete assessments. After the EOS visit, all subjects will be referred for continuation of their care as determined by the investigator. Additionally, for subjects who complete the study or discontinue for tolerability or lack of efficacy reasons, the sponsor will provide support for approved ADHD medication costs for up to 3 months after participation in the study, if deemed medically appropriate by the subject's healthcare provider.

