11.4.1. Adverse Events

Adverse events will be collected for each subject. Parents/guardians should be queried in a non-leading manner, without specific prompting (if the child has complained about changes in health and how the child has been feeling). Subjects should also be queried in a non-leading manner, without specific prompting (e.g., "How have you been feeling? Have you felt different?"). See [Section 12](#), Safety Reporting

AEs and SAEs will be monitored throughout the study at all visits starting after the first dose of study drug.

Untoward medical occurrences that occur prior to the first dose of study drug will be collected as pre-treatment events.

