11.5.2. Double-blind Period

11.5.2.1. Visit 4 (Day 1): First Laboratory Classroom Day

At this visit the subject should arrive at the clinic by 6:30 AM and the following study-related procedures will be performed:

- Record prior and concomitant medications
- Review inclusion/exclusion criteria
- Measure weight, record BMI
- Collect vital signs once.
- Administer C-SSRS since last visit version
- Collect samples for UDS, urine pregnancy test for females ≥ 8 years of age
- Randomize to treatment
- Dispense study drug
- Provide dosing diary
- Conduct 7 classroom sessions according to a Laboratory Classroom Manual common to all investigational sites.

Subjects will begin taking double-blind study drug on the evening of Day 1 at approximately 8 PM plus or minus 30 minutes. The first dose of study drug may be administered in the clinic, after all assessments are completed, or at home.

During the double-blind period, the clinical site will attempt to contact the subject's parent/legal guardian daily with a reminder to administer study drug.

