13. TERMINATION OF SUBJECT FROM STUDY/DISCONTINUATION OF STUDY DRUG

13.1. Criteria for Subject Termination

Subjects may terminate the study participation at any time for any reason.

The possible reasons for the termination of study participation are as follows:

- Adverse event.
- Lack of efficacy (specify).
- Lost to follow-up (specify).
- Pregnancy.
- Withdrawal by subject (specify).
- Non-compliance with study drug (specify).
- Protocol deviation (specify).
- Death.
- Other (specify).

If at any time during the course of the study, in the opinion of the Investigator, the subject may no longer safely participate due to a change in medical status (e.g., experiences an AE, becomes pregnant), the subject must be discontinued from the study treatment.

The reason for discontinuation and information will be recorded on the appropriate CRF. In case of death, the date of death should be captured on the CRF.

Subjects who prematurely terminate the study participation may be replaced.

Subjects who discontinue study drug prior to completion will be asked to return to the clinic and complete the EOS visit 7 (\pm 2) days later ([Section 11.5.3](#)).

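### All 14 doses precede the first scheduled post-dose safety enquiry, while the daily contact with the parent is described only as a dosing reminder

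*Protocol*

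**What the plan says.** **Dosing.** Section 11.5.2.1 sets the start: "Subjects will begin taking double-blind study drug on the evening of Day 1 at approximately 8 PM plus or minus 30 minutes". Section 7.1 sets the length: "Subjects will take one dose each evening before bedtime for a total of 14 days". Section 10.1 fixes the end: "On Day 14, the night before the second classroom day, study drug must be taken at approximately 8 PM plus or minus 30 minutes".

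**Scheduled safety checks.** Section 11.4.1 states: "AEs and SAEs will be monitored throughout the study at all visits starting after the first dose of study drug". After randomization the visits in Table 2 are Visit 4 (Day 1), Visit 5 (Day 15) and Visit 6 (Day 21 ± 2), and AE monitoring is marked only at Visits 5 and 6. SAP Appendix 14.1 repeats this pattern.

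**Contact during dosing.** Every day the site will attempt to contact the "parent/legal guardian daily with a reminder to administer study drug" (Section 10.2; likewise the Synopsis, 7.1 and 11.5.2.1). No AE question is mentioned in any of these places. The dosing diary records dose dates and times, and only the Day 14 entry goes into the database (Section 9.5).

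**Discontinuation.** Section 13.1 begins "If at any time during the course of the study, in the opinion of the Investigator, the subject may no longer safely participate", and then requires that study treatment be discontinued.

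**The concern.** The investigator's decision under Section 13.1 can be needed on any day of dosing, but no scheduled step brings information about the child to the investigator before the last dose. A problem that the parent does not volunteer is first asked about on Day 15.

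Two things are at stake. The first is timing: an event that might have mattered to the decision to continue can surface only after dosing has ended. The second is data quality. AE incidence and AEs leading to discontinuation are listed endpoints (Section 6.2), and SAP 8.4 calculates onset relative to first dose and derives duration from the onset date. For events not volunteered earlier, those dates and the severity grade depend on recall over as long as two weeks. Where the day of onset is not known and the month is that of the first dose, SAP 8.1 sets onset to the date of the first dose.

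**Working it through.** **Inputs** (Protocol 7.1, 10.1, 11.5.2.1, 11.5.2.2, Table 2): dose *k* at about 8 PM on Day *k*; first dose Day 1, last dose Day 14; Visit 5 arrival 6:30 AM on Day 15.

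**1. The plan's own dose count.** Day 1 to Day 14 inclusive is 14 − 1 + 1 = 14 doses, as stated. Seven days after Day 14 is Day 21, which agrees with Visit 6 in Table 2.

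**2. Where the checks fall relative to dosing.**

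| Check | Before first dose | Between dose 1 and dose 14 | After dose 14 |
|---|---|---|---|
| AE enquiry | none (pre-treatment events only) | none | Visits 5, 6 |
| Vital signs, C-SSRS | Visits 1, 2, 4 | none | Visits 5, 6 |
| Weight | Visits 1, 4 | none | Visits 5, 6 |
| ECG, hematology/chemistry, urinalysis, physical and neurological examination | Visit 1 | none | Visit 6 |

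The Day 1 checks count as pre-dose because the first dose follows completion of that day's assessments (Section 11.5.2.1).

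**3. Doses before and after the first post-dose check.** All 14 dose times are earlier than 6:30 AM on Day 15, so 14 doses precede it and 14 − 14 = 0 follow it.

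**4. Intervals.** 8 PM back to 6:30 AM on the same day is 13.5 h.
- First dose to Visit 5 arrival: 14 × 24 − 13.5 = 322.5 h, or 322.5 / 24 = 13.4 days.
- Last dose to Visit 5 arrival: 24 − 13.5 = 10.5 h (10 to 11 h with the ± 30 minute window).

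**5. A child who stops early.** The End of Study visit is 7 ± 2 days after the last dose (Section 11.5.3), so it too comes after dosing.

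**6. If the daily contact carried an AE question.** Contacts on Days 2 to 14 that come before the Day 14 dose number 14 − 2 + 1 = 13 per child, against 0 scheduled enquiries now. With 100 children all dosed to Day 14 this is at most 13 × 100 = 1,300 enquiries. Both figures are ceilings, because the protocol promises an attempt at contact rather than contact.

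**The case against.** The best case for the plan is that it is consistent and has safeguards between visits. Much of that stands, and it rules out several stronger readings that a reader might infer.

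- **That the schedule contradicts the promise of monitoring throughout the study.** It does not. Section 11.4.1 ties AE monitoring to visits, and Table 2 matches. Section 13.1 depends on the investigator's opinion and does not presuppose a scheduled check. This is a design choice that can be improved.
- **That harm cannot be detected or dosing cannot be stopped.** The documents say otherwise. Unscheduled visits are allowed (7.1). Blood pressure and pulse are taken if orthostatic symptoms appear (11.4.3). AEs are collected from first dose to last visit (12.1.1). SAEs are reported as soon as the site learns of them (12.4.1). Interruption and withdrawal of drug are recognized actions (12.3), and a DSMB reviews safety (7.1, 12.5). But for an individual child, most of these wait for someone to raise a problem, and DSMB review is not a scheduled per-child check during dosing.
- **That sites telephone daily and do not ask how the child is.** The mode of contact is not stated and no script is in the documents. A site may well ask; the plan does not require it or say that the answer is recorded.
- **That the earlier classroom study shows a comparable hazard at this dose.** Section 4.3 reports: "TEAEs associated with discontinuation were hallucinations (2 cases in the 6 mg/day group, 1 case in the 4 mg/day group"; also insomnia (1 at 4 mg/day), decreased appetite (1 at 6 mg/day) and rash (1 at 4 mg/day). That is 3 cases at 6 mg/day and 3 at 4 mg/day; the section reports no 2 mg/day arm for that study. In the other pediatric study, 2 mg/day had fewer TEAEs, related TEAEs and discontinuation TEAEs than 4 mg/day, though more than placebo, and there were no SAEs. The documents do not say how any of these events came to light.
- **That accumulation measures the problem.** Section 4.3 gives a median half-life of 56 to 84 hours, so drug levels build up over the two weeks. An accumulation ratio describes drug level and does not count missed or delayed harms. The same section reports that apparent oral clearance was highest in the lowest dose group, so that half-life range need not apply at 2 mg.

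**Conclusion.** The point holds for scheduled, per-child checks: 14 of 14 planned doses come before the first scheduled post-dose safety enquiry or measurement, and the contact already attempted each day has no stated safety content. This rests on the visit schedule and on dosing as planned, with no assumption about pharmacology.

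The consequence is modest but real. Events that are not volunteered surface after dosing has ended, and their onset and severity rest on recall over up to 14 days. The documents give no figure for how many events would be missed or delayed, so none is offered. Nothing here says that 2 mg/day is unsafe. The primary analysis, sample size and power are unaffected. It is a worthwhile low-cost improvement.

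**What to change.** In Protocol 10.2, 11.4.1, 11.5.2.1 and Table 2, state that:

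- the daily contact during dosing includes the non-leading AE question already given in Section 11.4.1;
- any event reported is entered on the AE CRF with its onset date;
- it is made known to the investigator under the protocol's existing AE procedures.

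The matching sentences in the Synopsis and Section 7.1, and SAP Appendix 14.1, should follow. The mode of contact should also be stated.

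No stopping or dosing rule is proposed. Clinical decisions stay with the investigator under Section 13.1, and the timing of vital signs, weight and C-SSRS is unchanged, so this closes the gap for enquiry but not for measurement.

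**Cost.** No new visit. There is some extra site time and data entry, and more if the reminder is not now given by voice. Asking daily may bring in more mild AEs in both arms, which could make AE rates less comparable with the earlier studies.
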